### 9.1.1.1 Screening

Screening Visit assessments are listed in [Table 3-1](#).

Screening will occur within 28 days before administration of study drug. If the time between screening and dosing exceeds 28 days as a result of unexpected operational delays (e.g., delayed drug shipment), then subjects do not require rescreening if the Day -1 laboratory results meet the eligibility criteria.

Subjects will be instructed on the study restrictions ([Section 9.4](#)).

A subject who qualified but did not enroll for an earlier cohort may be used in a subsequent cohort with no required rescreening if the Day -1 laboratory results meet the eligibility criteria and if all other screening data were obtained within 28 days before administration of study drug.

Individual subjects may enroll in up to 2 cohorts (either 2 cohorts in Part A or 1 cohort in Part A and 1 cohort in either Part B or Part C) if at least 21 days has elapsed between the last dose of study drug in the first cohort in which they participate and the first dose of study drug in the next cohort. All screening assessments must be completed again and eligibility confirmed for participation in the next cohort.

Subjects who do not meet the eligibility criteria may not be rescreened, with the following exceptions, all of which require principal investigator approval:

- Subjects who met all eligibility criteria but had an intercurrent illness (e.g., upper respiratory infection with fever) in the 14 days before the first study drug dose that was properly evaluated and which resolved fully
- Subjects who met all eligibility criteria but were not able to obtain required documentation within the allotted screening window
- Subjects who met all eligibility criteria but transiently (for personal reasons) are unable to commit to all study procedures

- Subjects who met all eligibility criteria but are not randomized for administrative reasons (e.g., study drug is not available at the study site)
- If applicable, subjects who were screened under a prior version of the protocol and did not meet any exclusion criterion, with the exception of a criterion that was updated in a subsequent version of the protocol

Repetition of any screening assessment that did not meet eligibility criteria is not permitted, unless there is clear evidence of a laboratory error or a damaged specimen (e.g., hemolysis of sample).

The medical monitor should be notified of any decisions made regarding rescreening or retesting.

#### **9.1.1.2 Treatment Period**

Subjects will be admitted on Day -1 and will remain in the clinical research unit (CRU) for the duration of the Treatment Period.

Treatment Period assessments are listed in [Table 3-2](#) (Cohorts A1 through A6 [up to A8]), [Table 3-3](#) (Cohort A3), [Table 3-4](#) (Cohort A9), [Table 3-5](#) (Part B), and [Table 3-6](#) (Part C).

The treatment periods for Part A, B, and C will be conducted as described in [Section 9.1.1](#). Dosing details are given in [Section 9.6.1](#).

If a subject has any clinically significant, study-related abnormalities at the conclusion of a scheduled inpatient portion of the study, the medical monitor (or authorized designee) will be notified, and the subject will be asked to remain in the CRU until such abnormalities resolve. If the subject is unable or unwilling to remain in the CRU, the medical monitor (or authorized designee) will be notified, and the investigator will make every effort to arrange follow-up evaluations at appropriate intervals to document the course of the abnormalities.

#### **9.1.1.3 Follow-up**

Subjects will have a Safety Follow-up Visit 7 to 10 days after the last study drug dose. Safety Follow-up Visit assessments are listed in [Table 3-2](#) (Cohorts A1 through A6 [up to A8]), [Table 3-3](#) (Cohort A3), [Table 3-4](#) (Cohort A9), [Table 3-5](#) (Part B), and [Table 3-6](#) (Part C).

#### **9.1.1.4 Early Discontinuation**

Subjects who prematurely discontinue study drug dosing will be asked to return to the CRU for a Safety Follow-up Visit. Safety Follow-up Visit assessments are listed in [Table 3-2](#) (Cohorts A1 through A6 [up to A8]), [Table 3-3](#) (Cohort A3), [Table 3-4](#) (Cohort A9), [Table 3-5](#) (Part B), and [Table 3-6](#) (Part C).

Subjects who discontinue from study drug dosing for any reason (except withdrawal of consent) will have a final PK blood sample drawn as soon as possible after the decision to discontinue study drug is made. Additional safety assessments may also be performed at the discretion of the investigator, including possible consultation with a specialist consultant. The Vertex medical monitor will be informed about these additional assessments, and any additional data collected (e.g., as the result of an outside consultation) will be considered part of the study record to provide the most complete safety profile of the study drug.

## 9.1.2 Part D (Subjects With CF)

A schematic of the study design for Part D is shown in [Figure 9-1](#), which has a randomized, double-blind, placebo-controlled, parallel-group design. After completing the Screening Period, approximately 12 subjects will be randomized 3:1 to TC:placebo.

Screening in Part D will be initiated after the completion of Parts A, B, and C (cohorts needed for Part D dose selection only) through the Safety Follow-up Visit. The decision to proceed to Part D will be based on an evaluation of safety, tolerability, and PK data from completed cohorts in Parts A, B, and C. These data will be submitted to the IEC for approval before proceeding to screening for Part D. Refer to [Section 9.3.2](#) for additional details.

**Figure 9-1 Schematic of Study Design for Part D**

Screening Period 4 weeks	Treatment Period a 4 weeks	Safety Follow-up Period 4 weeks
	N = 9 VX-121 + TEZ/IVA	
	N = 3 Placebo	

a The planned VX-121 dose for Part D is 10 mg qd. This dose is predicted to provide an approximate AUC0-24h of 10 µg·h/mL, which is within the predicted efficacious exposure range based on in vitro data. Based on emerging safety, tolerability, and PK data from Parts A, B, and C, the planned dose for Part D may be lowered to 5 mg qd. The total daily dose of VX-121 in Part D will be at least 1 dose level below the highest total daily dose tested in Part C. The dosage of TEZ/IVA in the TC will be TEZ 100 mg qd/IVA 150 mg q12h, which will be administered as TEZ 100 mg/IVA 150 mg FDC in the morning and IVA 150 mg in the evening.

### 9.1.2.1 Screening

Screening Visit assessments are shown in [Table 3-7](#).

The Screening Period will occur within 28 days before the first dose of study drug. The site investigator (or designee) will confirm and document study eligibility before randomization.

#### 9.1.2.1.1 Repetition of Screening Assessment(s)

Repetition of individual screening assessment(s) that did not meet eligibility criteria is not permitted with the following exceptions:

- If there is clear evidence of a laboratory error, damaged specimen (e.g., hemolysis of sample), or equipment malfunction, collection of a repeat sample for the appropriate laboratory test or assessment is permitted.
- Exclusionary liver function test (LFT) levels may be retested once within 14 days of the original screening date. The Vertex medical monitor should be made aware of the repeat testing.
- Assessments required for eligibility may be repeated if permitted, as described in [Section 8.2](#).

If screening spirometry measurements fail to meet acceptability and repeatability criteria as specified by American Thoracic Society/European Respiratory Society guidelines, repeat spirometry evaluation may be performed once.

If repeat values of the individual assessment(s) are within the eligibility criteria and completed within the screening window, then the subject is eligible for the study.

### **9.1.2.1.2 Rescreening**

Subjects may be rescreened only once. If a subject is rescreened, all screening assessments will be repeated except for *CFTR* genotyping, follicle-stimulating hormone (FSH) level (if serum FSH level was  $\geq 40$  mIU/mL during prior screening), and sweat chloride level. If a subject is rescreened, the new screening window will begin once the first rescreening assessment has been initiated.

### **9.1.2.1.3 Extension of Screening Period Window**

The Screening Period window may be extended by 2 weeks for the following reasons:

- Repetition of the Screening Period assessments ([Section 9.1.2.1.1](#))
- Unexpected operational or logistic delays, or to meet the eligibility criteria
- Repetition of spirometry assessment if results are of poor quality

### **9.1.2.2 Treatment Period**

The Treatment Period will last approximately 4 weeks. Subjects will be evaluated as outpatients.

Study visits during the Treatment Period will occur as shown in [Table 3-7](#). All visits will occur within the windows specified. Study drug administration details are provided in [Section 9.6.2](#).

Subjects must meet both of the following conditions to qualify to continue into the Treatment Period:

- Must have stable CF disease (as judged by the investigator) and have remained on a stable CF medication regimen during the 28 days before the Day 1 Visit. (For example, subjects cannot have an acute upper or lower respiratory infection, pulmonary exacerbation, or changes in therapy [including antibiotics] for pulmonary disease within 28 days before the first dose of study drug in the Treatment Period.)
- Must not have had an acute non-CF illness (e.g., gastroenteritis) within the 14 days before the first dose of study drug in the Treatment Period.

If these conditions are not met, subjects may not be randomized and enter into the Treatment Period.

Randomization will occur before the first dose of study drug during the Treatment Period and will occur on the Day 1 Visit (or Day -1) after conditions for entry into the Treatment Period have been confirmed.

### **9.1.2.3 Follow-up**

Subjects will have a Safety Follow-up Visit approximately 28 days after the last study drug dose. Safety Follow-up Visit assessments are listed in [Table 3-7](#).

#### **9.1.2.4 Early Termination of Treatment**

If the subject prematurely discontinues study drug, an Early Termination of Treatment (ETT) Visit should be scheduled as soon as possible after the subject decides to terminate study drug. Subjects who prematurely discontinue study drug will also be required to complete the Safety Follow-up Visit, approximately 28 days after their last dose of study drug. The assessments performed at the Safety Follow-up Visit are listed in [Table 3-7](#).

Subjects who discontinue from study drug dosing for any reason (except withdrawal of consent) will have a final PK blood sample drawn as soon as possible after the decision to discontinue study drug is made. Additional safety assessments may also be performed at the discretion of the investigator, including possible consultation with a specialist consultant. The Vertex medical monitor will be informed about these additional assessments, and any additional data collected (e.g., as the result of an outside consultation) will be considered part of the study record to provide the most complete safety profile of the study drug.

If the ETT Visit occurs 3 weeks or later following the last dose of study drug, then the ETT Visit will replace the Safety Follow-up Visit, and a separate Safety Follow-up Visit will not be required.

If the subject withdraws consent for the study, no further evaluations should be performed, and no additional data should be collected. Vertex may retain and continue to use any data and samples collected before such withdrawal of consent.

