**Table 3-7 Study VX17-121-001: Part D, Screening, Treatment Period, and Safety Follow-up Visit**

Event/Assessment a	Screening Visit b	Treatment Period c				ETT Visit d	Safety Follow-up 28 (± 7) Days After Last Dose of Study Drug
	Days -28 to -1	Day 1	Day 8 (± 1 day)	Day 15 (± 1 day)	Day 29 (± 1 day)		
Outpatient visits	X	X	X	X	X	X	X
Informed consent	X						
Randomization e		X					
Demographics	X						
Medical history	X						
Weight f	X	X	X	X	X	X	X
Height f	X						
Vital signs g	X	X	X	X	X	X	X
Pulse oximetry g	X	X	X	X	X	X	X
Physical examination h	Complete	Abbreviated	Abbreviated	Abbreviated	Abbreviated	Abbreviated	Complete
Standard 12-lead ECG i	X	X	X	X	X	X	X
Sweat chloride j,k	X	X	X	X	X	X	X
Spirometry l	X	X	X	X	X	X	X
Urinalysis j	X	X	X	X	X	X	X
Serum β-hCG (all female subjects)	X						

a All assessments will be performed before dosing, unless noted otherwise. Assessments that are collected before and after dosing will only be collected once if study drug is not administered on the day of the visit (i.e., premature discontinuation of study drug treatment).

b All screening results must be reviewed before randomization, unless noted otherwise.

c To qualify to continue into the Treatment Period, conditions for entry must be satisfied ([Section 9.1.2.2](#)).

d If the subject prematurely discontinues study drug, an ETT Visit should be scheduled as soon as possible after the decision to terminate study drug treatment. Additional PK samples and safety assessments may also be performed at the discretion of the investigator. See [Section 9.1.2.4](#) for additional details.

e Randomization may occur on the previous day (Day -1) after all conditions for entering the Treatment Period have been confirmed ([Section 9.1.2.2](#)).

f Weight and height will be measured with shoes off.

g Vital signs and pulse oximetry will be collected after the subject has been at rest for at least 5 minutes.

h Complete and abbreviated PEs are described in [Section 11.7.3](#).

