**Table 3-7 Study VX17-121-001: Part D, Screening, Treatment Period, and Safety Follow-up Visit**

Event/Assessment a	Screening Visit b	Treatment Period c				ETT Visit d	Safety Follow-up 28 ( $\pm$ 7) Days After Last Dose of Study Drug				
	Days -28 to -1	Day 1	Day 8 ( $\pm$ 1 day)	Day 15 ( $\pm$ 1 day)	Day 29 ( $\pm$ 1 day)						
CFTR genotype m	X										
FSH n	X										
Serum chemistry and hematology j	X	X	X	X	X	X	X				
Coagulation j	X	X	X	X	X		X				
PK sampling p		X	X	X	X	X					
Randomized study drug dosing q		Day 1 through Day 29									
Adverse events	Continuous from signing of ICF through Safety Follow-up Visit										
Medications review r	Continuous from signing of ICF through Safety Follow-up Visit										
Treatment and procedures review	Continuous from signing of ICF through Safety Follow-up Visit										

m CFTR genotyping will be performed for all subjects. If the screening CFTR genotype result is not received before randomization, a previous CFTR genotype laboratory report may be used to establish eligibility.

n FSH will be measured for any suspected postmenopausal female subjects with at least 12 months of continuous spontaneous amenorrhea.

p Blood samples will be collected for PK analysis of VX-121, TEZ and metabolites, and IVA and metabolites. On Day 1, samples will be collected before dosing (0 hours) and at 1, 2, 4, and 6 hours after dosing (relative to the morning dose). On Days 8 and 29, a predose sample will be collected before the morning dose of study drug (0 hours). On Day 15, samples will be collected before dosing (0 hours) and at 1, 2, 4, 6, and 8 hours after dosing. Acceptable PK sampling windows are provided in Table 11-1. At the ETT Visit, a single blood sample for PK analysis will be collected.

q The last dose of study drug will be the morning dose on the Day 29 Visit.

r All medications taken from 28 days before the Screening Period through the end of the study will be recorded.

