#### **12.3.4 Safety Analysis**

Safety is the primary objective of this study. The overall safety profile of VX-121 will be assessed in terms of the following primary (safety) endpoints:

- Incidence of treatment-emergent adverse events (TEAEs)
- Clinical laboratory values (including coagulation studies)
- ECG outcomes

- Vital signs
- Spirometry (Part D only)

Safety analyses will be based on the Safety Set. No statistical hypothesis testing will be conducted.

For safety variables, the baseline value will be defined as the most recent non-missing measurement collected before the initial administration of study drug.

All safety data will be presented in individual subject data listings.

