12 APPENDICES

Appendix A: Analysis Visit Windows (Part D Only)

Table 12-1 Analysis Visit Windows for Safety and Efficacy Assessments

Assessment	Visit ¹	Target Study Day	Analysis Visit Window ^{2,3,4} (in study days)
Safety Assessment			
Serum Chemistry	Baseline	1	≤1 Pre-dose
Hematology	Day 8	8	(1 ⁵ , 12]
Coagulation	Day 15	15	(12, 22]
Vital Signs (including Weight and BMI)	Day 29	29	(22, 43]
	Safety Follow-up	Not applicable	Use nominal visit
Standard 12-lead ECG	Baseline	1	≤1 Pre-dose
	Day 1 Postdose	Not applicable	Use nominal visit
	Day 8	8	(1, 12]
	Day 15 Predose and Postdose	Not applicable	Use nominal visit
	Day 29		(22, 43]
	Safety Follow-up	29	Use nominal visit
		Not applicable	
Efficacy Assessment and Pharmacodynamic Assessment			
Spirometry	Baseline	1	≤1 Pre-dose
Sweat Chloride	Day 8	8	(1, 12]
	Day 15	15	(12, 22]
	Day 29	29	(22, 43]
	Safety Follow-up	Not applicable	>43

Table 12-1 Analysis Visit Windows for Safety and Efficacy Assessments

Assessment	Visit ¹	Target Study Day	Analysis Visit Window ^{2,3, 4} (in study days)
Notes:			
Visit name for analysis purpose is used to report data in tables and figures.			
2 The analysis visit windows will be applied using the following rules for both scheduled and unscheduled visits: 
 If no numerical measurement is available within a visit window, the measurement will be considered missing for the visit. If there is more than 1 numerical measurement available within a visit window, use the following rules: 
 The measurement closest to the target day will be used; or If there are multiple measurements with the same distance from the target day, the latest measurement will be used. 			
3 For lab, ECG and vital sign measurement collected on the date of first dose of study drug in Treatment Period, if it cannot be determined whether the measurement is before or after the first dose: 
 Scheduled measurement will be treated as pre-dose observation. Unscheduled measurement will be treated as post-dose observation. 			
4 For safety assessment, Safety Follow-up analysis visit will be based on nominal Safety Follow-up visit. If a subject doesn't have a nominal Safety Follow-up visit but has an ETT visit with study day >43, then the ETT visit will be mapped into Safety Follow-up analysis visit.			
Derived Variables:			

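### Part D: coagulation is not scheduled at the Early Termination of Treatment Visit, and a late one can replace Safety Follow-up without taking over its coagulation test or complete examination

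*Protocol*

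**What the plan says.** Protocol Section 9.1.2.4 asks for an ETT Visit as soon as possible once a Part D subject decides to stop study drug. The default is that the Safety Follow-up Visit still takes place: "Subjects who prematurely discontinue study drug will also be required to complete the Safety Follow-up Visit, approximately 28 days after their last dose". There is one exception, which applies when the ETT Visit is held at least 21 days after dosing ended: "then the ETT Visit will replace the Safety Follow-up Visit, and a separate Safety Follow-up Visit will not be required". Nothing in the section says which assessments are done at an ETT Visit that serves in this way. Additional safety assessments are left to the investigator's discretion.

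Protocol Table 3-7 sets the content of each visit. The chemistry and hematology row, "Serum chemistry and hematology j X X X X X X X", has seven marks. The coagulation row, "Coagulation j X X X X X X", has six, and the empty cell is in the ETT column. The examination row reads "Physical examination h Complete Abbreviated Abbreviated Abbreviated Abbreviated Abbreviated Complete", so the examination is abbreviated at ETT and complete at Safety Follow-up.

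Protocol Section 12.3.4 names "Clinical laboratory values (including coagulation studies") among the primary safety endpoints. SAP Section 9.4.2 summarises Part D coagulation at each scheduled time point, and SAP Appendix D gives threshold criteria for PTT and for PT/INR. Note 4 to SAP Table 12-1 covers a subject who has no nominal Safety Follow-up Visit but has an ETT Visit after study day 43: "then the ETT visit will be mapped into Safety Follow-up analysis visit".

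**The concern.** Two parts of the plan do not fit together. The ETT Visit has a shorter test list than the Safety Follow-up Visit, yet under one condition it is allowed to stand in for it. The item left out belongs to a panel that the protocol counts within its primary safety endpoints. No footnote explains the omission, and blood is already drawn at ETT for chemistry and hematology.

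What is at stake is a uniform coagulation result in subjects who stop early. Without a scheduled draw, whether a result exists near the time of stopping depends on whether the subject attends a later treatment visit off drug, or on whether the investigator chooses to order the test.

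**Working it through.** The documents give no figure to reproduce. The check sets the schedule against the replacement rule and does the date arithmetic.

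**Step 1: Table 3-7, selected rows.**

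| Assessment | Screening | Day 1 | Day 8 | Day 15 | Day 29 | ETT | Safety Follow-up |
|---|---|---|---|---|---|---|---|
| Chemistry and hematology | X | X | X | X | X | X | X |
| Coagulation | X | X | X | X | X | blank | X |
| Physical examination | Complete | Abbrev. | Abbrev. | Abbrev. | Abbrev. | Abbrev. | Complete |

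Weight, vital signs, pulse oximetry, ECG, spirometry and urinalysis are also marked at ETT. Coagulation is the only repeated safety assessment that is not.

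**Step 2: the two paths after early stopping.** The Safety Follow-up window is 28 ± 7 days after the last dose, which is 21 to 35 days. The replacement rule starts at 3 weeks = 21 days, the lower edge of that window.

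- ETT less than 21 days after the last dose: no scheduled coagulation at ETT. The Safety Follow-up Visit is still required, with coagulation and a complete examination. Only the result at ETT is missing.
- ETT 21 days or more after the last dose: no scheduled coagulation at ETT and no Safety Follow-up Visit. No closing coagulation result is scheduled, and the closing examination is abbreviated.

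**Step 3: treatment visits that could still supply a result.** Let d be the study day of the last dose, and take visits at their nominal days.

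| Last dose | Next visit with coagulation | Days after last dose |
|---|---|---|
| d = 1 to 7 | Day 8 | 8 − d = 7 to 1 |
| d = 8 to 14 | Day 15 | 15 − d = 7 to 1 |
| d = 15 to 28 | Day 29 | 29 − d = 14 to 1 |

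The longest gap is 14 days (15 with the +1-day visit window), which is less than 21. So a coagulation visit always falls between the last dose and the earliest replacing ETT Visit. A subject has no scheduled result after stopping only if that visit is missed and the ETT Visit is also late.

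**Step 4: where the SAP places a replacing ETT Visit.** The earliest such visit is on study day d + 21.

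| Last dose | Study day d + 21 | SAP Table 12-1 window |
|---|---|---|
| d = 1 | 22 | Day 15, (12, 22] |
| d = 2 to 22 | 23 to 43 | Day 29, (22, 43] |
| d = 23 or later | 44 or later | Safety Follow-up, by note 4 |

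Note 4 therefore applies only to some replacing ETT Visits. In each row of this table, the schedule provides no coagulation value from the ETT Visit.

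**Step 5: weight of one subject.** Part D plans about 12 subjects, with 9 on triple combination. One affected subject is 1/12 = 8.3% of Part D or 1/9 = 11.1% of the active arm. These are the weights of a single subject, not expected rates. The documents give neither a discontinuation rate nor a frequency of late ETT Visits.

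**The case against.** The best counter-argument is that the plan already yields a coagulation result in most cases. Safety Follow-up remains mandatory unless the ETT Visit is late, and ETT is meant to happen as soon as possible. Step 3 shows that a treatment visit with coagulation falls inside the 3 weeks. Footnote a to Table 3-7 provides for visits at which drug is not given because of premature discontinuation, and Protocol Section 9.9 says that subjects withdrawn from treatment continue to be followed. Protocol Section 11.7.2 adds further laboratory tests where clinically appropriate. The word replace might also be read as the ETT Visit becoming the Safety Follow-up Visit, assessments included.

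Most of this stands and limits the point. It does not remove it. Section 9.1.2.4 does not expressly require attendance at the remaining treatment visits, discretionary testing does not give a uniform result, and the reading of replace is not written down.

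A reader might infer more than the documents support:

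- That early stoppers in general have no coagulation result after treatment. This is not so; it takes a late ETT Visit and a missed intervening visit, with no additional test.
- That SAP note 4 maps the ETT Visit to a cell where no value can exist. This is not so either. SAP Section 9.1 and Table 12-1 admit unscheduled measurements, so a discretionary result could be analysed.
- That the missing results depend on why the subject stopped, for example under the liver criteria of Protocol Section 9.8.2, so that threshold tables understate abnormalities. The blank cell applies whatever the reason, and Section 9.8.2 requires close follow-up with confirmatory testing, although it does not name coagulation.
- That the abbreviated examination affects a summary. Examination results are only listed (Protocol Section 12.3.4.5, SAP Section 9.4.6).

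**Conclusion.** The point holds in a limited form. Every Part D subject who stops early lacks a scheduled coagulation result at the ETT Visit. In the uncommon case of an ETT Visit 3 weeks or later after the last dose, no closing coagulation result is scheduled and the closing examination is abbreviated. When that visit is also after study day 43, the SAP maps it to Safety Follow-up although the schedule provides no coagulation value for it.

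The impact is small: about 12 subjects, descriptive safety analysis, and few subjects likely to meet the 3-week condition. No claim is made that missing results depend on the reason for stopping. The point is worth acting on because coagulation sits within the primary safety endpoints and the repair is cheap.

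The conclusion assumes that the blank ETT cell is intended as it stands. The neighbouring row lines up across all seven columns, which supports that. The footnote letters on the same page of the table skip from n to p, so the cell should be confirmed against the source table before the amendment is drafted.

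**What to change.** Reconcile Table 3-7 with Protocol Section 9.1.2.4 in two places:

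1. In Table 3-7, mark coagulation in the ETT column.
2. In Section 9.1.2.4, add a sentence such as: When the ETT Visit replaces the Safety Follow-up Visit, all Safety Follow-up assessments in Table 3-7, including coagulation and the complete physical examination, will be performed at the ETT Visit.

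SAP note 4 needs no change, since the schedule would then supply the coagulation value that it maps.

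The cost is one table cell and one sentence in the protocol, one extra tube at a blood draw that already takes place, and a complete rather than abbreviated examination for the few subjects with a replacing ETT Visit. No endpoint or analysis method changes.
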